6.1.3 Real World (at-home) Wearable Devices Assessments

Wearable devices capture and records high resolution raw acceleration data, which is converted into a variety of objective activity and sleep measures using both proprietary and publicly available algorithms. Data obtained will be used to evaluate performance (Gait and Sit-to-stand) and activity level (Steps and Activity Bouts; Intensity, and Energy Expenditure; Body Position; Sleep Onset)

Lumbar Sensor

The lumbar sensor will be applied at each in-lab visit and will be continued to be worn at home for a 7-day period following the in-lab visits (baseline, week 6, week 12 and week 18), , after which they will be mailed back. If the visit occurs at-home the participant will be mailed the sensor with instructions on application. The data will be processed using previously developed algorithms (e.g., GaitPy).

Proposed Device: Axivity AX6- 6-Axis Logging Accelerometer. Recording frequency: 100Hz.

Endpoints:

Gait measures	
Cadence (steps/min)	
Step length symmetry	
Gait speed (m/s)	
Stride duration (s)	
Stride duration asymmetry (s)	
Step duration (s)	
Step duration asymmetry (s)	
Initial double support time (s)	
Terminal double support time (s)	
Total double support time (s)	
Single limb support time (s)	
Stance time (s)	
Swing time (s)	
Step length (m)	
Sit to stand measures	
Number of sit-to-stands	
Duration (s)	
Maximum acceleration (m/s ²)	
Minimum acceleration (m/s ²)	
SPARC: SPectral ARC length	

Wrist-worn sensor

The wrist sensor will be applied at the first in-lab (baseline) visit and continuously worn on the non-dominant wrist throughout the entire duration of the study. If the visit occurs at-home the participant will be mailed the wrist sensor and given verbal and written instructions on how to wear the device.

Proposed Device: ActiGraph GTx9. Recording frequency: vendor's default.

Endpoints:

- Steps/day
- Time spent in moderate and vigorous physical activity (MVPA) (min)
- % wear-time in MVPA

- Sedentary time (min)
- % wear-time sedentary

6.1.4 Questionnaires

Baseline Only Questionnaires:

KOOS

KOOS is a widely utilized self-reported measures of lower extremity symptoms and function. It provides scores on symptoms, pain, activities of daily living, quality of life, and sports and recreation. The instrument will be administered as the 5-level Likert scale (0=none, 1=slight, 2=moderate, 3=very, 4=extremely). The KOOS in its entirety will be administered at baseline.

Mobile Device Proficiency Questionnaire (MDPQ)

The MDPQ was designed to assess the mobile device proficiency of older adults as technology proficiency has become increasingly important to perform activities of daily living (Roque et al, 2018). We will use the short version of the MDPQ which consists of 16 questions to assess participants' proficiency when using a mobile device with answers ranging from "1-Never tried" to "5-Very easily" resulting in a total score ranging from 16 to 90. We expect that higher scores of proficiency will translate into increased study compliance.

Multidimensional Outcome Expectations for Exercise Scale (MOEES)

The MOEES is a 15-item questionnaire that quantifies outcome expectations from following an exercise program (Wojcicki et al, 2009). For each item, participants indicate the degree to which they agree with each statement on a scale of 1 (*strongly disagree*) to 5 (*strongly agree*). The questions convey the overall expected effect of exercise on items such as strength, mood and overall health. Scores range from a minimum of 15 to 75. Higher scores are indicative of higher levels of outcome expectations for exercise and therefore hypothesized to be associated with higher physical exercise adherence and self-efficacy.

Center for Epidemiologic Studies Depression scale (CES-D)

The CES-D scale is a commonly used self-report measure of depressive symptoms (Radloff et al, 1977). It consists of 20 items each scored from 0 ("rarely") to 3 ("most or all of the time") with a total possible score of 60.

Modified Charlson Comorbidity Index

A modified version of the self-reported Charlson Comorbidity Index will be used that assesses the number and severity of various health conditions.

Repeated Questionnaires

KOOS-Remaining

KOOS is a widely utilized self-reported measures of lower extremity symptoms and function. It provides scores on symptoms, pain, activities of daily living, quality of life, and sports and recreation. The instrument will be administered as the 5-level Likert scale (0=none, 1=slight, 2=moderate, 3=very, 4=extremely). The KOOS in its entirety will be administered at baseline. The Sports/Recreation, Quality of Life, and Symptom subscale (except stiffness questions) will be administered at week 6, week 12, and week 18.

Treatment history

This includes x

Pain Survey:

This questionnaire includes the following sections. The pain survey will be administered at baseline, week 6, week 12, and week 18.

- 3-item pain catastrophizing scale: The Pain Catastrophizing Scale (PCS) is a 13-item self-report measure of catastrophizing in the context of actual or anticipated pain (Sullivan et al, 1995). The PCS measures catastrophizing in 3 facets: rumination, magnification and helplessness. It is a self-report measure and consists of 13 items, which are scored from 0 to 4 and result in a total possible score of 52. It has been studied in many acute and chronic pain cohorts and elevated scores have been found to correlate with pain severity and sensitivity, pain chronicity and disability. A short version consisting of 3 items will be utilized therefore with a total possible score of 12.
- Widespread Pain Index: A 4-question widespread pain index will be used to assess the severity of fatigue, trouble thinking or remembering, waking up tired, and other physical symptoms.
- Joint homunculus for number of painful joints: A body map will be used to identify all painful joints. A joint homunculus has been used to identify widespread pain and has been validated in numerous epidemiologic studies.
- Modified painDETECT©: The *painDETECT©* questionnaire is a patient-completed screening tool designed to detect neuropathic-like components in patients with chronic pain using a scoring system that ranges from 0 to 38. The PDQ has associated with neuropathic-like pain symptoms in different clinical scenarios, including osteoarthritis, lower back pain, fibromyalgia and malignancy (Freynhagen et al, 2006). Scores lower than 12 indicate a neuropathic-like component to be unlikely, whereas scores greater than 19 indicate a likely neuropathic-like component. A modified version that only includes questions 11-13 will be used.

Daily Questionnaires:

Daily Sleep Interference Scale (DSIS)

The Daily Sleep Interference Scale (DSIS) quantifies sleep interference due to pain and is an 11-point scale that asks the participant to "select the number that best describes how much your pain has interfered with your sleep during the past 24 hours" (Vernon et al, 2008). Response options range from 0 (Did not interfere with sleep) to 10 (Completely interfered with sleep/unable to sleep due to pain). Negative change from baseline scores indicate improvement (lessening) of how much pain interfered with sleep.

Medication log

This question will ask about whether the participant has taken any analgesic medications for joint pain or arthritis.

Exercise and activity log

This survey asks about the amount of physical activity (in minutes) performed by the participant and whether they completed their physical therapy home exercise program each day.

Weekly Questionnaires:

KOOS-Weekly

KOOS is a widely utilized self-reported measures of lower extremity symptoms and function. It provides scores on symptoms, pain, activities of daily living, quality of life, and sports and recreation. The instrument will be administered as the 5-level Likert scale (0=none, 1=slight, 2=moderate, 3=very, 4=extremely). The Pain and Function subscales, plus two questions on stiffness from the Symptom subscale will be administered each week.

Patient's Global Assessment of OA (PGA-OA)

PGA is commonly used for patient assessment of global health or of disease activity. In our study, participants will be asked to evaluate their impression of pain severity and global impact on daily activities by answering to the following question: *Considering all the ways your osteoarthritis in your knee affects you, how are you doing today?*; Participants will rate their condition using a 5-point Likert scale (1=very good, 2=good, 3=fair, 4=poor, 5=very poor).

Numeric Rating Scale for Pain with Nominated Activity (NRSna)

The NRSna is a single-item instrument that evaluates self-reported pain with the advantage of allowing individual variability as participants are asked to nominate an activity that most aggravates their pain and then providing a rating score within that context (Parkes et al, 2016). Participants will be asked to *"select an activity that is most troublesome due to your knee pain"* and will subsequently rate their knee pain over the past week during this activity using a numeric rating scale that ranges from 0 (zero – no pain at all) to 10 (worst imaginable pain).

Demographics

Demographical data including ethnicity, race, education, income, smoking history, employment status, insurance information, marital status, and weight history will be obtained at baseline assessment.

Week-18 Only Questionnaire:

Exit Survey

This questionnaire will include items on:

- Effect of PT: This will include questions on overall effect of PT, participant enjoyment with PT, and ratings of the intervention and interventionists. All questions will be asked using a 5-point Likert scale.
- Feedback on study: Participants will be asked to provide feedback on various aspects of the study including time commitment, in-lab testing, etc.
- Sensor comfort: Participant will be asked to provide feedback on their comfort with the sensors used in the study.

7. ANALYSIS PLAN

7.1. Analysis of Primary Aim and Endpoints

Details of the analysis of this study will be documented in the Statistical Analysis Plan (SAP). The analyses described in the approved SAP will be followed if different from what is described in this protocol.

Primary Aim: Measure the effect of PT on functional performance using digital measures from wearable sensors.

The following analyses will be performed to address this primary aim.

A. Validate wearable sensor-based metrics of functional biomechanical tests in people with knee OA against optical motion capture

Data from the lumbar sensor and optical motion capture during gait and sit-to-stand tasks during in-lab visits will be used for this analysis. Wearable sensor metrics will be compared against gold standard metrics from the optical motion capture system using intra-class correlation coefficient (ICC) and its 95% lower and upper confidence limits. The ICC reflects both the degree of correlation and agreement between the measurements. We will interpret agreement between measurements according to the following benchmarks: $ICC \leq 0.4$ indicates 'poor', 0.4 to 0.59 'moderate', 0.6 to 0.74 'good', and 0.75 to 1 'excellent' reliability (Cicchetti et al., 1994). In addition, we will also compute the mean, variance and percentage error between the standard and the digital measurements. Bland–Altman plots and 95% limits of agreement (average difference ± 1.96 standard deviation of the difference) will also be computed.

B. Compare wearable sensor-based metrics of physical performance in people with knee OA with standardized physical performance outcomes.

Wearable sensors with excellent reliability from analysis A will be examined. Sensor-based metrics from lumbar sensor during physical performance tests in-lab will be correlated with standardized physical performance outcomes using Pearson's product-moment correlations or Spearman's rank order correlations depending on their normality.

C. Assess the effects of exercise-based PT on outcomes from wearable sensors during in-lab physical performance tests

Wearable sensors with excellent reliability from analysis A will be examined. Mixed model repeated measures (MMRM) analysis will be used to investigate the effect of PT on endpoints derived from the lumbar sensor during in-lab physical performance tests. The outcome measures will be expressed as the change from baseline at each visit (i.e. 6 and 12 weeks). The model will include the baseline value of the outcome variable, week (as a categorical factor), and the interaction between the baseline value and week, as well as covariates such as age, sex, BMI, and presence of comorbidities. Unstructured covariance matrix will be assumed for the model errors. If visual inspection of the model diagnostics (i.e. residuals) suggest that a transformation of the endpoint should be performed, this will be applied as appropriate prior to analysis (i.e. change from baseline would be calculated on the transformed scale) and documented in the final report as required. The Least Squares Means (LSMeans) together with 95% confidence intervals will be obtained for each week and plots will be produced illustrating the trajectory of the LSMeans over time. The above outputs will be back-transformed to the original scale for transformed endpoints as required. Missing values will be accounted for by utilizing a maximum likelihood-based approach as part of the MMRM assumptions.

The primary analyses will be applied to each endpoint separately. The Benjamini-Hochberg procedure will be used to control the false discovery rates (FDR). FDR will be set at 5% and adjusted p-values (i.e., q values) < 0.05 will be considered significant.

Sensitivity analyses will include (a) only in participants who attended at least 80% (14 visits) of the PT visits, and (b) in all participants stratified into < 6 PT visits attended, 6-12 PT visits attended, and >12 PT visits attended.

D. Assess the effects of exercise-based PT on outcomes from wearable sensors during at-home activities

Wearable sensors with excellent reliability from analysis A will be examined. The same MMRM approach and sensitivity analyses described above will be used to investigate change from baseline to 6- and 12-weeks with PT on at home endpoints. Mean/median across a valid period for each endpoint will be used in the analyses.

E. Assess the effects of exercise-based PT in-lab tests of physical performance.

The same MMRM approach and sensitivity analyses described above will be used to investigate change from baseline to 6- and 12-weeks with PT on physical performance outcomes.

F. Assess the effects of exercise-based PT using joint mechanics during in-lab functional biomechanical tests

The same MMRM approach and sensitivity analyses described above will be used to investigate change from baseline to 6- and 12-weeks with PT on endpoints derived from optical motion capture during in-lab visits.

Details of any sensitivity or supportive analyses, along with details of any multivariate analyses (i.e. including more than one endpoint in an analysis) will be fully documented and specified in the SAP.

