1. STUDY SUMMARY

1.1. Synopsis

This will be a longitudinal, single arm, 19-week study to investigate the utility of digital assessments to measure the efficacy of physical therapy (PT) for reducing pain and improving function in people with knee osteoarthritis (OA).

A total of 60 participants will be included. Participants will receive a supervised exercise-based PT for 12 weeks and will undergo multiple assessments of strength, balance, gait and joint movement while being monitored with a motion capture system and wrist and lumbar wearable sensors. Additionally, participants' activities will be monitored in the real world with the same wrist and lumbar wearable sensors. After completion of the PT program, participants will be monitored for an additional 6-week period to measure persistence of treatment effect. During that time, they will continue to follow an exercise program at home.

The primary objective will be to measure the effect of PT on functional performance and pain reduction using both patient reported outcomes questionnaires (PROs) and digital metrics obtained from the laboratory assessments and wearable sensors worn in the real world. Pain phenotyping questionnaires and quantitative sensory testing assessments will also be used to evaluate the effect of specific pain phenotypes in treatment response.

A substudy will be undertaken to assess reproducibility of sensor-based measures during physical performance testing across at-home and in-lab implementation, as well as, reproducibility of these measures over repeated at-home implementation.

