2. INTRODUCTION

Current evidence indicates that PT interventions can reduce pain and improve function in people with knee OA. PT may result in improvement by several mechanisms including decreasing knee joint load, altering lower limb alignment, improving range of motion and restoring neuromuscular function (Page et al, 2011), thereby allowing people with knee OA who have been previously inactive due to their pain to participate in greater volume and intensity of activity. Increased activity has its own benefits in terms of improved fitness and quality of life, however, the type of activity and the nature of mechanical loading in joints that have been underutilized due to chronic pain may, in part, determine whether that change is productive or detrimental to joint health. Therefore, improved joint mechanics and kinematics may reduce the risk of negative outcomes such as rapidly progressing joint degeneration or outright injury potentially caused by increased activity in a previously underutilized joint.

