4. STUDY DESIGN

4.1. Overall Study Design

Participants with baseline pain during weight-bearing activities due to their knee OA will be recruited to a 19-week study. Eligible participants will be assessed at baseline and will undergo a supervised exercise-based PT program for 12 weeks as well as multiple in-lab functional assessments of strength, balance, pain, and gait while being monitored with an optical motion capture system, inertial motion capture system, surface EMG, and two wearable sensors at the wrist and lumbar areas (Actigraph and Axivity, respectively). Additional study visits will occur at week 6 and week 12 (end of PT). Participants' activities will be continuously monitored in the real world with the wrist sensor for the total duration of the study and for week-long periods with the lumbar sensor. There will be an additional 6-week monitoring period to measure persistence of treatment effect (i.e., week 12 to 18). The final in-lab visit will occur at the end of 18-weeks and the final at-home assessment with the lumbar and wrist sensors will occur in week 19. In case, in-lab visits are not possible due to COVID-19, a modified protocol will be used to collect outcomes remotely.

4.2.

Sample Size Calculation

The sample size calculation for this study was based on the traditional primary outcome for OA studies, i.e. the WOMAC pain and function scores. A successful digital endpoint can detect changes with treatment with a smaller sample size than the WOMAC. Meta-analyses of published RCTs on land-based therapeutic exercise compared with a non-exercise control report (Fransen et al, 2015) an effect size of 0.49 (95%CI 0.39-0.59) for improvements in pain immediately post-treatment and an effect size of 0.52 (95%CI 0.39-0.64) for improvements in function immediately post-treatment. To account for potential differences in study populations and intervention protocols, we used conservative effect sizes of 0.40 for both pain and function outcomes. Given this effect size, assuming a significance level of 0.05 with a two-tailed distribution and power of 80%, the total sample size estimated for a paired t-test analysis is 52 for a single-arm study. Accounting for an expected 10% attrition, we would need 57 participants. Hence, the proposed sample size of 60 should be sufficient to detect significant changes in the WOMAC scores (traditional primary outcomes).

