Sensitivity analyses will include (a) only in participants who attended at least 80% (14 visits) of the PT visits, and (b) in all participants stratified into < 6 PT visits attended, 6-12 PT visits attended, and >12 PT visits attended.

D. Assess the effects of exercise-based PT on outcomes from wearable sensors collected at-home

The following definitions will be used for analysis of at home sensor data. Based on the literature, a recording day will be considered valid and included in the analysis if it contains at least 10 waking hours (identified using the Cole-Kripke algorithm implemented in ActiLife software) of wear-time. At-home wrist and lumbar sensor data will be summarized on a weekly basis. A week of recording will be included in the analysis if there is at least 4 valid days (as described above) in a 7-day period.

A subset of wearable sensor metrics for gait and sit-to-stand from Section 3.1. E. that are shown to have excellent reliability from analysis A, and the physical activity measures from Actigraph (Section 3.1. E) will be examined. Since *number of gait bouts* derived from free living data is not assessed in

the lab, this will be automatically included in this analysis. The same MMRM approach and sensitivity analyses described above will be used to investigate change from baseline to 6- and 12-weeks with PT on at home sensor endpoints. Mean/median for each endpoint (depending on the distribution of the endpoint) across a valid period will be used in the analyses.

E. Assess the effects of exercise-based PT in-lab tests of physical performance.

The same MMRM approach and sensitivity analyses described above will be used to investigate change from baseline to 6- and 12-weeks with PT on all physical performance outcomes described in Section 3.1. D.

F. Assess the effects of exercise-based PT using joint mechanics during in-lab functional biomechanical tests

The same MMRM approach and sensitivity analyses described above will be used to investigate change from baseline to 6- and 12-weeks with PT on all endpoints derived from optical motion capture system (Gait: Table 1. Column 2; Sit-to-stand: Table 2. Column 2; Section 3.1. C) during in-lab visits.

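### At-home gait is reduced to one pooled value per week, so a change in the mix of short and long walking bouts cannot be separated from a change in gait itself

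*Protocol*

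**What the plan says.** Protocol 7.1 D sends the at-home endpoints to the same MMRM as the in-lab ones (change from baseline to weeks 6 and 12) and summarises them by this rule: "Mean/median across a valid period for each endpoint will be used in the analyses". SAP 4.2 D repeats it with one addition: "Mean/median for each endpoint (depending on the distribution of the endpoint) across a valid period will be used in the analyses".

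The SAP's validity rules act on days (at least 10 waking hours of wear) and weeks (at least 4 valid days in 7), not on bouts. Neither document sets a minimum bout length, bout-length strata, a weighting unit, or an adjustment for walking volume. The named MMRM covariates are age, sex, BMI and comorbidities, besides baseline value and week. The sensitivity analyses concern PT attendance only.

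The number of gait bouts is an endpoint in SAP 3.1 E; bout duration is not. Protocol 6.1.3 places gait and sit-to-stand under performance, and steps and activity bouts under activity level. The Protocol Introduction expects PT to allow previously inactive people "to participate in greater volume and intensity of activity".

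**The concern.** A weekly mean or median of gait speed, cadence, step length or a support time depends on two things: how a person walks in bouts of a given length, and how much of the recorded walking falls in bouts of each length. The second is behaviour, and it may change in a trial whose treatment is expected to raise activity. If long bouts are faster than short ones, someone whose gait is unchanged but who takes more long walks shows a higher weekly gait speed. Someone who makes more short trips shows a lower one. A fixed in-lab task does not have this problem.

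At stake is the interpretation of the primary aim for the at-home gait metrics: better walking, or a different pattern of walking. The ambiguity carries forward, because Secondary Aims 1B and 3 take up only at-home metrics with a significant week-12 change. The single-arm design offers no comparison group to help resolve it.

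**Working it through.** **The plan's own figure.** Protocol 4.2 uses an effect size of 0.40, two-sided alpha 0.05 and 80% power, and states that "the total sample size estimated for a paired t-test analysis is 52 for a single-arm study". Exact noncentral-t power is 79.99% at n = 51 and 80.8% at n = 52, so 52 reproduces. For attrition, 52 × 1.1 = 57.2 (stated 57) and 52 / 0.9 = 57.8; the planned 60 covers both. This calculation is for WOMAC pain and function, so it neither supports nor weakens the present point.

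**Inputs.** The summary rule and the absence of bout-level rules come from the documents. Everything numerical about bouts is assumed: a long-minus-short speed gap of 0.1-0.4 m/s, a shift in long-bout share of 5-20 percentage points, and an SD of change of 0.05-0.12 m/s.

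**Formula.** With no change in gait at either bout length, change in pooled mean = (change in long-bout share) × (speed gap). The share must be expressed in the unit being averaged. If that unit is walking time:

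| Gap (m/s) | 5 points | 10 points | 20 points |
|---|---|---|---|
| 0.1 | 0.005 | 0.010 | 0.020 |
| 0.2 | 0.010 | 0.020 | 0.040 |
| 0.3 | 0.015 | 0.030 | 0.060 |
| 0.4 | 0.020 | 0.040 | 0.080 |

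**In SD units.** A shift of 0.02 m/s is 0.40, 0.25 or 0.17 SD at an SD of change of 0.05, 0.08 or 0.12 m/s. At n = 52 the chance of an unadjusted p < 0.05 is then 81%, 42% or 22%.

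**Dependence on the averaging unit.** Take a 10-point shift (30% to 40% of walking time), gaps of 0.2-0.4 m/s, and n = 54 (60 less 10%).
- Time-weighted: the shift is 0.02-0.04 m/s. With noise SD 0.09 m/s and SD 0.10 for the share change, the total SD is √(0.09² + (gap × 0.10)²) = 0.092-0.098. That is 0.22-0.41 SD, giving p < 0.05 in 35-83% of trials.
- Each bout counted equally, assuming long bouts last 120 s and short ones 15 s: the share of bouts goes from (0.30/120) / (0.30/120 + 0.70/15) = 5.1% to (0.40/120) / (0.40/120 + 0.60/15) = 7.7%. The shift is 0.026 × 0.2-0.4 = 0.005-0.010 m/s, or 0.06-0.12 SD at SD 0.09, giving p < 0.05 in about 7-13%.

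**Median.** In a two-component mixture (short bouts at 0.8 m/s, within-component SD 0.15, gap 0.2), moving the long share from 20% to 30% shifts the median by 0.020 m/s, the same as the mean.

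**Opposite direction.** A real gain of 0.03 m/s is cancelled if the long-bout share falls by 0.03/0.3 = 10 points to 0.03/0.1 = 30 points.

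**Effect of standardising.** In simulation (4,000 runs, n = 52, 10-point shift in the averaging unit, gaps 0.1, 0.2 and 0.3 m/s, no mean change within bands), the pooled mean gave p < 0.05 in 27%, 75% and 96% of runs. The fixed-weight mean gave about 5%. That 5% follows from how the standardised mean is built; the simulation confirms only that the method removes the mix component.

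**The case against.** The strongest reply is that the pooled value may be exactly what is wanted. Objective 3 concerns PT's impact on real-world activities and performance, and the SAP's definition of physical function includes physical activity at home. If PT leads someone to take longer, faster walks, that person's usual gait speed has changed. A reader might infer that such a change is a false positive and that the pooled value should be replaced. The documents do not support that: they do not restrict analysis D to walking capacity. This part of the objection stands, and the pooled endpoint should stay.

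Other parts also stand. Pooling over every detected bout is the plain reading of a rule with no bout-level restriction, but it is not stated, and any minimum bout built into the algorithm is not described. The Introduction predicts more activity, not a different mix of bout lengths; more walking in the same mix has no effect. The percentages above use unadjusted p-values, whereas the plan applies Benjamini-Hochberg at 5%. The 0.40 planning effect is not a benchmark for gait.

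It is also true that analyses C, E and F measure ability under fixed conditions, and that bout counts, steps and MVPA are analysed separately. None of these splits the at-home gait value into mix and within-bout gait. The ICC filter in analysis A cannot do so either, since it uses in-lab tasks only, and false-discovery control does not address a systematic shift.

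**Conclusion.** The point holds as a gap in interpretation, not as a demonstrated bias. The plan labels gait as performance, anticipates more activity, and has no analysis that shows whether a change in at-home gait arose within bouts or from their mix. The possible shift of about 0.005-0.08 m/s rests wholly on the assumed speed gap and change in time share, and its direction is unknown. It is much smaller under equal weighting of bouts, and zero if gait does not vary with bout length or the mix is stable. A reader might take the 35-83% as the plan's error rate; it is not, because it depends on assumed inputs, time weighting and raw p-values. The point is limited to the lumbar gait metrics and does not touch steps per day or MVPA. A low-cost supportive analysis is justified; a change of the main at-home analysis is not.

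**What to change.** In SAP 4.2 D:

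1. Keep the pooled weekly value as the planned real-world gait endpoint. Define a bout, including any minimum length, and state the averaging unit (bout, stride or time).
2. Add a prespecified supportive MMRM on gait metrics computed within bout-duration bands fixed before follow-up data are examined. Combine the bands with the same weights at every visit, for example the cohort's pooled baseline distribution. Each participant's own baseline shares would be a poorer choice, since someone with no long bouts at baseline would then give later long walks zero weight.
3. State a rule for empty bands.
4. Report band shares by visit.
5. Say beforehand what counts as agreement between the two analyses. Attribute an at-home gait change to functional performance only where the standardised result agrees, including for metrics carried into Secondary Aims 1B and 3. Otherwise describe it as a change in real-world walking behaviour.

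The cost is SAP wording and modest processing, since bouts are already detected for the bout-count endpoint. Visits, devices and sample size are unchanged. The standardised estimates will be somewhat less precise where bands are sparse, and merging bands at some visits would weaken the fixed weighting, so the empty-band rule matters.
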